5.6.5. Physical Exam and Eastern Cooperative Oncology Group Performance Status

Physical examination abnormalities reported as AEs will be summarized along with other TEAEs.

Shift tables will be used to summarize the count and frequency for each shift of baseline ECOG performance status grade to the worst and the best post-baseline ECOG grade. The ECOG performance status grades are outlined in Table 4.

All physical examination findings and ECOG performance status results will be presented in data listings.

Table 4 Eastern Cooperative Oncology Group Performance Status Grades

Grade	Description
0	Normal activity. Fully active, able to carry on all pre-disease performance without restriction.
1	Symptoms, but ambulatory. Restricted in physically strenuous activity, but ambulatory and able to carry out work of a light or sedentary nature (e.g., light housework, office work).
2	In bed < 50% of the time. Ambulatory and capable of all self-care, but unable to carry out any work activities. Up and about more than 50% of waking hours.
3	In bed > 50% of the time. Capable of only limited self-care, confined to bed or chair more than 50% of waking hours.
4	100% bedridden. Completely disabled. Cannot carry on any self-care. Totally confined to bed or chair.
5	Dead.

Source: Oken MM, Creech RH, Tormey DC, et al. Toxicity and response criteria of the Eastern Cooperative Oncology Group. Am J Clin Oncol. 1982; 5:649-655

5.6.6. Electrocardiogram

The actual value and change from baseline at each time point will be summarized for 12-lead ECG parameters. The 12-Lead ECG parameters include heart rate, PR, RR, QRS, QT and QTcF intervals.

Categorical groups of QTcF will be summarized as follows:

- Maximum post-baseline QTcF
 - ≤ 450 msec
 - > 450 and ≤ 480 msec
 - > 480 and ≤ 500 msec
 - > 500 msec

- Maximum change from baseline for QTcF
 - ≤ 30 msec
 - > 30 and ≤ 60 msec
 - > 60 msec
- Baseline QTcF < 450 msec and post-baseline QTcF > 500 msec
- Baseline QTcF between 450 and 480 msec and post-baseline QTcF ≥ 530 msec

ECG parameters will be summarized by visit and the worst post-baseline change from baseline. All ECG data will be included in a by-participant data listing. Listings will be provided for participants with abnormal or outlying values for QTcF and changes in QTcF.

5.6.7. Vital Signs

The actual value and change from baseline for all parameters (blood pressure, respiratory rate, heart rate, and body temperature) will be summarized at each scheduled visit.

Potentially clinically significant post-baseline vital signs will also be summarized following the criteria as below:

- Systolic Blood Pressure (mmHg)
 - Value ≥ 150
 - Increase of 20 from baseline
 - Value ≥ 150 and increase of 20 from baseline
 - Value < 90
 - Decrease of 20 from baseline
 - Value < 90 and decrease of 20 from baseline
- Diastolic Blood Pressure (mmHg)
 - Value ≥ 95
 - Increase of 10 from baseline
 - Value ≥ 95 and increase of 10 from baseline
 - Value < 60
 - Decrease of 10 from baseline
 - Value < 60 and decrease of 10 from baseline

- Heart Rate (beats/min)
 - Value ≥ 110
 - Increase of 20 from baseline
 - Value ≥ 110 and increase of 20 from baseline
 - Value ≤ 50
 - Decrease of 20 from baseline
 - Value ≤ 50 and decrease of 20 from baseline
- Temperature (°C)
 - Value ≥ 38
 - Value < 35

Vital sign measurements will be summarized by visit and the worst post-baseline change from baseline. The data listing will be presented for each participant. A summary table and listing will also be provided for participants with potentially clinically significant vital signs.

5.6.8. Concomitant Medications

Any medication or vaccine (including over-the-counter or prescription medicines, vitamins, and/or herbal supplements) that the participant is receiving at the time of informed consent and/or receives during the study through 30 days after the last dose of study treatment will be recorded along with:

- Reason for use;
- Dates of administration including start and end dates; and
- Dosage information including dose and frequency.

Concomitant medications will be coded using the WHO Drug Dictionary March 2022 version or higher. Medications or vaccines that ended before receiving the first study treatment will be considered as the prior medication. Medications or vaccines that continued or started on or after receiving the first dose through 30 days after the last dose of study treatment will be summarized as the concomitant medication. Medication, vaccine or procedure started more than 30 days after the last dose will be considered as subsequent.

The handling of partial/missing start dates for concomitant therapies/medications are described in Section 4.9.2. Concomitant medications will be tabulated by anatomic therapeutic class (ATC) and PT. In these tabulations, each participant will contribute only once to each ATC and PT regardless of number of uses.

The concomitant procedures will be coded using the MedDRA coding dictionary version 27.0 and displayed in tables and data listings using system organ class (SOC) and preferred term (PT).

All medications, vaccines and procedures will be included in data listings. An identifier will be used to show whether a medication, vaccine or procedure was prior, concomitant or subsequent.

5.7. Pharmacokinetic and Pharmacodynamic Analyses

Exploratory analyses maybe conducted based on the data collected, with purposes of providing information for potential pharmacokinetic/pharmacodynamic (PK/PD) analysis if deemed necessary. The specifics of these analyses will be described in a separate PK/PD Analysis Plan and reported separately from the main Clinical Study Report (CSR). For purposes of the CSR for which this SAP provides the basis, serum pharmacokinetic collection dates, times, and concentrations will be displayed in a data listing. Additionally, summaries of the concentrations will be provided.

5.8. Interim Analysis

No formal interim analysis is planned. This study planned to use a Bayesian approach of continuous monitoring for early futility stopping based on ORR Potential timepoints for interim evaluation might occur when 10, 20, and 30 participants had completed 6 months of follow-up or dropped out. At each interim look, an exact 2-sided 95% CI based on the Clopper-Pearson method would also be provided. See Section 1.4 for a brief description of both methods.

This section provides detailed calculation of the Bayesian approach, however, due to the rapid enrollment, the previously planned informal data assessment using this Bayesian approach for early futility stopping based on ORR was no longer feasible as instead of 10 participants, 53 were already enrolled before the one year predicted cutoff time point.

The Bayesian approach to be used for futility analysis assumes a beta-binomial distribution with an uninformative prior of beta distribution. If a random variable Z follows a beta distribution with parameters (α, β) , the probability density function will be

$$(1) \quad f(z) = \frac{z^{\alpha-1}(1-z)^{\beta-1}}{B(\alpha, \beta)},$$

where potential values of z are in $(0,1)$,

$$(2) \quad B(\alpha, \beta) = \Gamma(\alpha)\Gamma(\beta)/\Gamma(\alpha + \beta),$$

and Γ is the Gamma function, i.e., $\Gamma(\alpha) = \int_0^{\infty} t^{\alpha-1} e^{-t} dt$. The mean of Z is $\alpha/(\alpha + \beta)$.

At the first interim look, the prior of ORR is assumed to follow a beta distribution with parameter $(0.1, 0.9)$. Hence the corresponding mean is 0.1. Assume at an assessment point, the study has accrued X responders out of n (<43) participants. With a prior distribution of *beta* (a, b) , X follows a binomial distribution and the posterior distribution of the response rate follows a beta distribution with parameters $(a+x, b+n-x)$, where x is the observed value of X ([Lee and Liu 2008](#); [Chen et al. 2019](#)). For example, if 2 out of 10 participants are responders at the first interim look, the updated prior of ORR will follow a beta distribution with parameters $(2.1, 8.9)$, which has a mean of $2.1/11=19.1\%$. Hence, the initially assumed beta prior with parameters $(0.1, 0.9)$ does not have substantial impact on the updated prior and is considered non-informative prior.

For the remaining $(43-n)$ future participants, the number of responses, Y , follows a beta-binomial distribution with parameters $(43-n, a+x, b+n-x)$ ([Lee and Liu 2008](#)). Since a, b, n, x are known at this point, the probability $\Pr(Y=i)$ can be calculated using the probability mass function of a beta-binomial distribution. See equation (3) below.

If Z follows a beta-binomial distribution with parameters (n, a, b) , the probability of $Z = z$ is:

$$(3) \quad f(z|n, a, b) = \binom{n}{z} \frac{B(z+a, n-z+b)}{B(a, b)}$$

If i out of $(43-n)$ future participants are responders, the updated prior for ORR will follow a beta distribution with parameters $(0.1+x+i, 0.9-x-i)$. If under the frequentist framework, the null hypothesis is $\text{ORR} = 15\%$. the posterior probability of $\text{ORR} > 15\%$ can be calculated. Using SAS[®] CDF function, this probability is:

$$(4) \quad \text{pr}(ORR > 0.15|x, Y = i) = 1 - CDF(\text{"Beta"}, 0.15, (0.1 + x + i), (0.9 + 43 - x - i)).$$

Define the predictive probability as the chance of observing any $Y = i$ responders in future participants such that the posterior probability of $ORR > 0.15$ is greater than 85%. If the predictive probability is too low, e.g., $\leq 10\%$, the study may be terminated for futility.

From the observed responders x and a target ORR, the predictive probability of reaching the target ORR at the end of study can be calculated with the beta-binomial distribution as follows. After observing a total of x out of n responders up to an interim look, the possible number of responders, Y , in the future will be $0, 1, 2, \dots, (43 - n)$. For each possible $Y = i$, calculate the posterior probability of $Pr_i(ORR > 0.15|x, Y = i)$, where $i = 0, 1, 2, \dots, (43 - n)$, using equation (4). If this posterior probability is > 0.85 , $Y = i$ responders is considered promising. The probability of $Y = i$ can be calculated using equation (3). The predictive probability for $ORR > 15\%$ with threshold 85% is:

$$(5) \quad \text{Predictive probability}$$

$$= \sum_{i=0}^{43-n} \{ \text{pr}(Y = i|x) \times I[\text{pr}(ORR > 0.15|x, Y = i) > 0.85] \},$$

where $\text{pr}(Y = i|x)$ is the probability of observing i responders in future $(43 - n)$ participants given x out of n responders, and $I[\text{pr}(ORR > 0.15|x, Y = i) > 0.85] = 1$ if the statement inside [] is true; otherwise, the value of I is 0. In summary, the predictive probability in equation (5) can be calculated using the following algorithm:

1) Assign predictive probability pp to 0.

2) For $i = 0$ to $43 - n$,

a. Calculate the posterior probability $ps = \text{pr}(ORR > 0.15|x, Y = i)$ using equation (4).

b. If $ps > 0.85$, do the following:

i. Calculate the probability of observing $Y = i$ conditional on observing x responders using the beta-binomial distribution with parameters $(43 - n, x + 0.1, n - x + 0.9)$, i.e.,

$$(6) \quad \text{Pr}(Y = i|x)$$

$$\begin{aligned}
 &= \binom{43-n}{i} \frac{B(i+x+0.1, 43-n-i+n-x+0.9)}{B(a,b)} \\
 &= \binom{43-n}{i} \frac{B(i+x+0.1, 43-i-x+0.9)}{B(x+0.1, n-x+0.9)}.
 \end{aligned}$$

- ii. Update predictive probability pp with $pp + \text{pr}(Y = i|x)$.
- c. After completing the loop in 2), the final pp is the predictive probability of ORR >0.15 with threshold 0.85.

In addition to using the Bayesian approach to calculate the predictive probability of observing a promising ORR, the frequentist approach will also be applied by generating the exact 95% CI of ORR based on the Clopper-Pearson method.

To evaluate the robustness of the observed result, the number of observed responders will be decreased and increased by 1, 2, and 3 (as long as the resulting ORR is between 0 and 100%) to repeat the analyses of ORR.

6. CHANGES TO PLANNED ANALYSES

Notable changes from the protocol-defined statistical analyses compared to this statistical analysis plan are described below:

- I. PFS-6 was redefined as a survival probability.
- II. Definitions and analysis method were added for PFS and OS.
- III. The planned informal interim analysis using the Bayesian approach for early futility stopping based on ORR was not performed. Due to this study's rapid enrollment, it was not feasible to perform the planned informal interim analysis using the Bayesian approach because, instead of 10 participants, 53 were enrolled before the one year predicted cutoff time point.
- IV. Additional preferred terms were added in electrolyte abnormalities – protocol Section 4.3 vs. SAP section 8.4.1.4.

8. APPENDICES

8.1. RECIST Criteria V1.1

For full guidelines, see RECIST Criteria v1.1 (Eisenhauer 2009).

Categorizing lesions at Baseline:

- Only participants with measurable disease (i.e., at least one measurable lesion) at screening are included.

Measurable lesion – Lesion that can be accurately measured in at least one dimension (longest diameter [LD]) in the plane of measurement is to be recorded) and with longest diameter at least twice the slice thickness and at least 10 mm when assessed by computed tomography (CT) or magnetic resonance imaging (MRI)

- Measurable disease will be assessed by CT or MRI.
- The same method of assessment (CT or MRI) and the same technique will be used to characterize each identified and reported lesion at screening and during follow-up.
- Target Lesions - up to 2 lesions per organ and 5 lesions in total, representative of all involved organs at Baseline.
- Non-target Lesion-All other lesions (or sites of disease) will be identified as non-target lesions and should also be recorded at baseline. Measurements of these lesions are not required, but the presence or absence of each should be noted throughout follow-up.

Methods of Measurement

CT or MRI must be used to measure target lesions selected for response assessment.

Conventional CT and MRI will be performed with cuts of 10 mm or less in slice thickness contiguously.

Recording Tumor Assessments

All sites of disease must be assessed at screening. Screening assessment must be done within 28 days of starting study treatment. For an adequate screening assessment, all required scans must be done within 28 days prior to first dose of study treatment and all disease must be documented appropriately.

At follow-up, disease site must be assessed using the method (CT or MRI) and same technique as screening, including consistent administration of contrast (CT only) and timing of scanning. If a change needs to be made the case must be discussed with the Sponsor.

Unequivocal new lesions will be recorded at follow-up time points. Measurement of new lesions is not required. If a new lesion is equivocal, for example because of its small size, continued therapy and follow-up evaluation will clarify if it represents truly new disease. If repeat scans confirm there is definitely a new lesion, then progression should be declared using the date of the initial scan.

Response Criteria: Evaluation of target lesions

Complete Response (CR):	Disappearance of all target lesions.
Partial Response (PR):	At least a 30% decrease in the sum of the LD of target lesions, taking as reference the baseline sum of LD.
Progressive Disease (PD):	At least a 20% increase in the sum of the LD of target lesions, taking as reference the smallest sum of LD recorded since the treatment started or the appearance of one or more unequivocal new lesions. In addition to the relative increase of 20%, the sum must also demonstrate an absolute increase of at least 5 mm.
Stable Disease (SD):	Neither sufficient shrinkage to qualify for PR nor sufficient increase to qualify for PD, taking as reference the smallest sum LD since the treatment started.

Evaluation of best overall response

The best overall response is the best response recorded from the start of the study treatment until disease progression/recurrence (taking as reference for PD the smallest measurements recorded since the start of study treatment). The participant's best response assignment will depend on the achievement of both measurement and confirmation criteria (defined below).

Time point response: participants with target disease

Target Lesions	Nontarget Lesions	New Lesions	Overall Response
CR	CR	No	CR
CR	Non-CR/non-PD	No	PR
CR	Not evaluated	No	PR
PR	Non-PD or not all evaluated	No	PR
SD	Non-PD or not all evaluated	No	SD
Not all evaluated	Non-PD	No	NE
PD	Any	Yes or No	PD
Any	PD	Yes or No	PD
Any	Any	Yes	PD

CR=Complete Response; NE=Not Evaluable; PD=Progressive Disease; PR=Partial Response; SD=Stable Disease.

Participants with a global deterioration of health status requiring discontinuation of study treatment without objective evidence of disease progression at that time will be classified as having “symptomatic deterioration”. Every effort should be made to document the objective progression even after discontinuation of treatment.

Confirmation

- **Confirmation of response:**
 - The main goal of confirmation of objective response is to avoid overestimating the response rate observed. In cases where confirmation of response is not feasible, it should be made clear when reporting the outcome of such studies that the responses are not confirmed.
 - To be assigned a status of PR or CR, changes in tumor measurements must be confirmed by repeat assessments that will be performed no less than 4 weeks after the criteria for response are first met.
- **Confirmation of SD:** in the case of SD, follow-up measurements must have met the SD criteria at least once after study entry (signing of Informed Consent Form [ICF]) at a minimum interval of 8 weeks.

Duration of overall response

- The duration of overall response is measured from the time measurement criteria are met for CR or PR (whichever status is recorded first) until the first date that recurrence

or PD is objectively documented, taking as reference for PD the smallest measurements recorded since the treatment started.

Duration of stable disease

- SD is measured from the start of the treatment until the criteria for disease progression are met, taking as reference the smallest measurements recorded since the treatment started.

8.2. FACT/NCCN Ovarian Symptom Index (FOSI) - Version 4

Below is a list of statements that other people with your illness have said are important. Please circle or mark one number per line to indicate your response as it applies to the past 7 days.

			Not at all	A little bit	Some-what	Quite a bit	Very much
GP1	I have a lack of energy		0	1	2	3	4
02	I have been vomiting		0	1	2	3	4
GP4	I have pain		0	1	2	3	4
GP2	I have nausea		0	1	2	3	4
01	I have swelling in my stomach area		0	1	2	3	4
GE6	I worry that my condition will get worse		0	1	2	3	4
GF7	I am content with the quality of my life right now		0	1	2	3	4
03	I have cramps in my stomach area		0	1	2	3	4

Instructions:*

1. Record answers in "item response" column. If missing, mark with an X
2. Perform reversals as indicated, and sum individual items to obtain a score.
3. Multiply the sum of the item scores by the number of items in the subscale, then divide by the number of items answered. This produces the symptom index score.
4. As with all FACIT questionnaires, a high score is good. Therefore, a score of "0" is a severely symptomatic patient and the highest possible score is an asymptomatic patient.

Subscale	Item Code	Reverse item?	Item response	Item Score
FOSI	GP1	4	-	=_____
	O2	4	-	=_____
	GP4	4	-	=_____
Score range: 0-32	GP2	4	-	=_____
	O1	4	-	=_____
	GE6	4	-	=_____
	GF7	0	+	=_____
	O3	4	-	=_____

Sum individual item scores: _____

Multiply by 8: _____

Divide by number of items answered: _____ =FOSI total score

8.3. Mock-up Tables, Listings, and Figure

Mock-up tables, listings and figures are in separate documents.

8.4. Safety Topics of Special Interest Preferred Terms

This appendix outlines the definition of treatment-emergent AESIs. Additional attention will specifically be given to the safety topics of special interest identified using SMQ or customized MedDRA queries based on MedDRA version 27.0.

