**Table 9: Adverse Events of Special Interest (AESI)**

Skin Rash (reported as AESI if clinically significant Grade 2 and all Grade <math>\geq 3</math>. Per CTCAE v5.0)
Maculopapular rash
Pruritic rash
Erythematous rash
Folliculitis
Hidradenitis suppurativa
Elevated Liver Enzymes (reported as AESI if Grade <math>\geq 2</math>, per CTCAE v5.0)
AST
ALT
Alkaline Phosphatase
Total bilirubin
Electrolyte Insufficiency (reported as AESI if Grade <math>\geq 3</math>, per CTCAE v5.0)
Hypophosphatemia
Hypokalemia
Hypomagnesemia
Drug Reactions (reported as AESI for any grade)
Allergic reaction
Anaphylaxis
(Drug) hypersensitivity
Ovarian Toxicity (reported as AESI for any grade)
Ovarian dysfunction
Ovarian disorder
Amenorrhea
Oligomenorrhea
Premature menopause
Ovarian failure
Skin Cancer (reported as AESI for any grade)
Basal cell carcinoma
Squamous cell carcinoma (of skin)
Keratoacanthoma
Actinic keratosis
Any other skin cancer

AESI = Adverse Event of Special Interest; ALT = Alanine aminotransferase; AST = Aspartate aminotransferase; CTCAE = Common Terminology Criteria for Adverse Events

Participants reporting AEs/AESIs/SAEs of ovarian toxicity will have hormone levels assessed every 3 months until event resolution (or for at least 90 days after discontinuing study treatment).

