5.6.3. Safety Topics of Special Interest

Safety topics of special interest have been identified based on review of safety data from prior studies with nirogacestat and include additional AEs beyond those specified in Protocol Section 11.3.1 as adverse events of special interest (AESIs). These safety topics of interest, including AESIs determined by the investigators for this study, will be summarized on separate tables. These safety topics, including AESIs, are defined for analysis purposes in different ways, including by using standardized MedDRA queries (SMQ) or customized MedDRA queries, and whether an investigator determined that an event was an AESI.

Unless specified otherwise, the incidence of AESIs based on the investigator's determination will be summarized by SOC and PT in tables and listed separately in participant data listings, and those by using defined lists of specific MedDRA PTs without regard to the investigator's designation of the reported event as an AESI will be summarized similarly.

For the safety topics of special interest (including AESIs) defined using standardized MedDRA queries (SMQ) or customized MedDRA queries, the specific MedDRA PTs for inclusion are all listed in Appendix 8.4 under the following groups. Safety topics for which narrow and broad terms are identified, only narrow terms are used for summary tables. The safety topics will be summarized by SOC and PT based on the Safety Analysis Set.

- Hypersensitivity
- Skin Disorder and Rash
- Hepatotoxicity
- Electrolyte Disorder
- Non-melanoma Skin Cancer
- Musculoskeletal Disorders
- Bone Fractures
- Mucositis/Stomatitis

- Hematologic Disorders
- Opportunistic Infections
- Central Nervous System Vascular Disorders
- Embolic and Thrombotic Events
- Cardiac Rhythm Disturbances
- Upper Respiratory Tract Infections
- Diarrhea

In addition to the summaries by SOC and PT as described above, separate summaries for concomitant medication use will be presented for the following safety topics:

- Hypophosphataemia (A subset of Electrolyte Disorder terms)
- Upper Respiratory Tract Infection
- Diarrhea
- Skin and Subcutaneous Rash (Broad and Narrow; a subset of Skin Disorder and Rash terms)
- Skin and Subcutaneous Rash (Narrow; a subset of Skin Disorder and Rash terms)

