8.4.1.4. Electrolyte Disorder

Selected treatment-emergent abnormally low electrolyte disorder adverse events will be summarized. The electrolyte disorder search definition is a custom MedDRA version 27.0 query based on selected terms from the Metabolism and nutrition disorders and Investigations SOCs. The PTs are as defined below for each electrolyte. The frequency table will be summarized by descending frequency of lab analyte and PT. A shift table will be generated for lab grades in hypocalcemia, hypercalcemia, hypomagnesemia, hypermagnesemia, hypokalemia, hyperkalemia, hyponatremia, and hypernatremia, as well as for clinical categorization in phosphate.

Lab Analyte	Pertinent PTs
Hypocalcemia:	Blood calcium decreased, Hypocalcaemia, Hypocalcaemic seizure
Hypomagnesaemia:	Blood magnesium decreased, Hypomagnesaemia
Hypophosphatemia:	Blood phosphorus decreased, Hypophosphataemia
Hypokalaemia:	Blood potassium decreased, Hypokalaemia, Hypokalaemic syndrome
	Blood sodium decreased, Hyponatraemia, Hyponatraemic coma,
Hyponatremia:	Hyponatraemic encephalopathy, Hyponatraemic seizure, Hyponatraemic syndrome

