8.4.1.5. Non-Melanoma Skin Cancers

The non-melanoma skin cancers search definition is a custom MedDRA version 27.0 query based on selected terms from the Skin neoplasms malignant and unspecified (excluding melanoma) HLT within the Neoplasms benign, malignant and unspecified (including cysts and polyps) SOC, plus the PT of Squamous cell carcinoma. The PTs are shown below:

Atypical fibroxanthoma	Neoplasm skin
Basal cell carcinoma	Neuroendocrine carcinoma of the skin
Basal cell carcinoma metastatic	Pilomatrix carcinoma
Basal cell naevus syndrome	Porocarcinoma
Basosquamous carcinoma of skin	Primary cutaneous adenoid cystic carcinoma
Bowen's disease	Sebaceous carcinoma
Carcinoma in situ of skin	Squamoproliferative lesion
Dysplastic naevus syndrome	Skin angiosarcoma
Eccrine carcinoma	Skin cancer
Epidermal naevus syndrome	Skin cancer metastatic
Keratoacanthoma	Skin neoplasm bleeding
Malignant sweat gland neoplasm	Skin squamous cell carcinoma metastatic

Marjolin's ulcer	Skin squamous cell carcinoma recurrent
Mastocytoma	Squamous cell carcinoma of skin
	Trichoblastic carcinoma
	Squamous cell carcinoma

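### SAP 8.4.1 presents its preferred-term queries as the protocol-specified AESIs, but they do not implement protocol Table 9: no grade cut-offs are applied, and some listed events are left out

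*SAP*

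**What the plan says.** Protocol Section 11.3.1 refers to Table 9 for the AESIs of this study. Three of its six groups carry a grade condition:

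- Rash: "Skin Rash (reported as AESI if clinically significant Grade 2 and all Grade" 3 or higher.
- Liver: "Elevated Liver Enzymes (reported as AESI if Grade" 2 or higher, covering AST, ALT, alkaline phosphatase and total bilirubin.
- Electrolytes: "Electrolyte Insufficiency (reported as AESI if Grade" 3 or higher, covering hypophosphatemia, hypokalemia and hypomagnesemia.

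Drug reactions, ovarian toxicity and skin cancer count at any grade. The skin-cancer group names actinic keratosis and ends with a catch-all for any other skin cancer.

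SAP 5.6.3 plans two AESI summaries. One tabulates and lists AESIs as determined by the investigator. The other uses fixed preferred-term lists, "without regard to the investigator's designation of the reported event as an AESI will be summarized similarly". Where a topic has narrow and broad terms, only narrow terms enter the summary tables.

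The term lists are in SAP 8.4, introduced with "This appendix outlines the definition of treatment-emergent AESIs". Section 8.4.1 is headed as the protocol-specified AESIs, and wider topics have their own Section 8.4.2. On electrolytes, 8.4.1.4 says "Selected treatment-emergent abnormally low electrolyte disorder adverse events will be summarized" and gives terms without grades. The skin-cancer query in 8.4.1.5 draws on the "Skin neoplasms malignant and unspecified (excluding melanoma) HLT".

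Among changes from the protocol, SAP Section 6 states "Additional preferred terms were added in electrolyte abnormalities" and compares them with protocol Section 4.3, the benefit/risk summary. It says nothing about grade cut-offs.

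**The concern.** Followed literally, 8.4.1 yields counts presented as protocol-specified AESIs for a set of events that is not the protocol's set. A Grade 1 ALT rise, a Grade 2 hypokalaemia and a Grade 1 rash all enter. A melanoma or an actinic keratosis does not.

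The clinical study report would then hold two AESI tabulations on different definitions, with nothing in the SAP to say that they differ on grade. A reader could take the query figure as the protocol-defined incidence. A reader who compared the two tables to see whether sites had missed reportable AESIs could be misled, because events below the Table 9 thresholds are mixed in. No primary or secondary endpoint is affected.

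**Working it through.** There is no planned figure to reproduce. The check sets Table 9 beside SAP 8.4.1, group by group. Write T for the participants with a Table 9 event and Q for those counted by the query. Assume each reported event codes to the corresponding listed term.

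| Group | Table 9 | SAP 8.4.1 query | Relation |
|---|---|---|---|
| Electrolytes | Three analytes, Grade ≥ 3 | Same three at any grade, plus hypocalcaemia and hyponatraemia; no narrow/broad split | T lies within Q |
| Rash | Five terms; clinically significant Grade 2 or any Grade ≥ 3 | The matching terms are all marked narrow and count at any grade; other narrow terms, such as alopecia, are added | T lies within Q |
| Liver | Four analytes, Grade ≥ 2 | ALT and AST increases marked narrow, any grade; alkaline phosphatase and bilirubin increases listed without the mark | Neither contains the other |
| Drug reactions | Any grade | Term list, any grade | No grade mismatch |
| Skin cancer | Any grade, including actinic keratosis and any other skin cancer | Melanoma excluded by construction; actinic keratosis not listed | Q can miss part of T |
| Ovarian toxicity | Any grade | Left out, with a stated reason | Q misses T, but this is disclosed |

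**Electrolytes and rash.** T lies within Q, so the query count is at least the Table 9 count. The two are equal only if no participant enters the query solely through a lower-grade event or an added term.

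**Liver.** Let A be the participants with a Grade ≥ 2 ALT or AST rise, and B those with a Grade ≥ 2 alkaline phosphatase or bilirubin rise, so T is A and B together. The narrow-only table contains A and adds Grade 1 ALT and AST rises and other narrow terms. It loses anyone in B with no narrow term. The sign of the difference is not fixed. This row depends on superscript narrow marks read from a PDF, so the two terms should be checked against the original.

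**Where grade appears elsewhere.**

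- SAP 5.6.2: TEAEs by maximum grade and at Grade ≥ 3, by system organ class and preferred term.
- SAP 5.6.3: a Grade 1–2 versus ≥ 3 split for a few topics, including hypophosphataemia and rash, but not liver, hypokalaemia or hypomagnesaemia.
- SAP 5.6.4 and 8.4.1.4: laboratory shift tables, by grade for potassium and magnesium and by clinical category for phosphate.

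Most grade information will therefore be printed. None of these outputs gives participants per AESI group at the Table 9 threshold for liver, for the electrolyte group as a whole, or for rash with clinically significant Grade 2. For example, someone with both ALT and AST raised appears under two preferred terms.

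**The case against.** The strongest reply is that a protocol-based AESI table already exists. Sites report AESIs under Table 9, so the investigator-determined table carries its grade rules, and SAP 5.6.3 says openly that the term-list summary ignores the investigator's designation. This stands, and it limits the point.

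Second, Table 9's cut-offs are worded as reporting rules. Protocol Section 12.3.2 prescribes no grade-filtered AESI analysis, and Section 11.3.1 allows further events to be identified. The SAP is therefore free to summarise more broadly. That also stands, but it does not justify calling the broader set protocol-specified when 8.4.2 exists for wider topics. Setting aside the site's designation is also not a statement that the grade thresholds are dropped.

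Third, the added electrolyte terms are declared in Section 6 and in the version history, and results are shown by analyte, so hypocalcaemia and hyponatraemia can be separated by eye. Agreed; that part is a matter of tidiness.

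Fourth, the mock-up tables are in separate documents (SAP 8.3), so the final labels are unknown. True; the criticism applies to the SAP as written.

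A reader might go further and infer that AESI incidence will be overstated. The documents do not support this. The investigator-determined table is unaffected, and the query lists err in both directions. Nor can a multiple be built from the hypophosphatemia rate of 22% in protocol Section 6.3: it comes from an earlier dose-finding study in advanced solid tumours, no Grade ≥ 3 share is given, and that topic already receives a Grade 1–2 versus ≥ 3 split.

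**Conclusion.** The mismatch is real but modest. SAP 8.4.1 claims to define the protocol's AESIs and does not. For electrolytes and rash, the query count can only equal or exceed the Table 9 count. For skin cancer, the query can miss events that Table 9 names or covers. For liver, the direction is undetermined, subject to checking the narrow marks. Section 6 does not disclose the missing grade cut-offs or the missing skin-cancer terms.

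The size cannot be computed from the documents, and the net direction across groups is open. The conclusion rests on reading 8.4.1 as written, on events coding to the matching preferred terms, and on sites following Table 9 when they designate AESIs.

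**What to change.** 1. In the 8.4.1 liver, electrolyte and rash query tables, add a row restricted to Table 9's terms and grades. For Grade 2 rash, use the investigator's AESI flag to identify clinical significance. Label the all-grade row as a broader safety topic.
2. Add melanoma and actinic keratosis terms to the skin-cancer query. Mark alkaline phosphatase and bilirubin increases as narrow, after checking the original PDF.
3. State in 8.4.1 and Section 6 that the preferred-term queries depart from protocol Table 9 / Section 11.3.1, and that the investigator-determined table gives the protocol-defined AESI incidence.

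Moving hypocalcaemia and hyponatraemia to 8.4.2 is optional.

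The cost is SAP wording, revised term lists and slightly longer safety tables. All the data are already collected.
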